6.9 Adverse events of specific interest

AEs of specific interest for safety monitoring include meningitis and potential Immune-Mediated Diseases pIMDs.

6.10 Potential immune-mediated diseases (pIMD)

pIMDs are a subset of AEs that include autoimmune diseases and other inflammatory and/or neurologic disorders of interest which may or may not have an autoimmune aetiology. AEs that need to be recorded and reported as pIMDs include those listed below. However, the investigator will exercise his/her medical and scientific judgment in deciding whether other diseases have an autoimmune origin (i.e. pathophysiology involving systemic or organ-specific pathogenic autoantibodies) and should also be recorded as a pIMD.

List of potential immune-mediated diseases:

Neuroinflammatory disorders
 
 • Cranial nerve disorders, including paralyses/paresis (e.g. Bell's palsy) • Optic neuritis • Multiple sclerosis • Transverse myelitis • Guillain-Barré syndrome, including Miller Fisher syndrome and other variants • Acute disseminated encephalomyelitis, including site specific variants: e.g. non-infectious encephalitis, encephalomyelitis, myelitis, myeloradiculoneuritis • Myasthenia gravis, including Lambert-Eaton myasthenic syndrome • Immune-mediated peripheral neuropathies and plexopathies, (including chronic inflammatory demyelinating polyneuropathy, multifocal motor neuropathy and polyneuropathies associated with monoclonal gammopathy). • Narcolepsy 	
Musculoskeletal disorders
 
 • Systemic lupus erythematosus and associated conditions • Systemic scleroderma (Systemic sclerosis), including diffuse systemic form and CREST syndrome • Idiopathic inflammatory myopathies, including dermatomyositis • Polymyositis • Antisynthetase syndrome • Rheumatoid arthritis, and associated conditions including juvenile chronic arthritis and Still's disease • Polymyalgia rheumatica • Spondyloarthritis, including ankylosing spondylitis, reactive arthritis (Reiter's Syndrome) and undifferentiated spondyloarthritis • Psoriatic arthropathy • Relapsing polychondritis • Mixed connective tissue disorder 	
Skin disorders
 
 • Psoriasis • Vitiligo • Erythema nodosum • Autoimmune bullous skin diseases (including pemphigus, pemphigoid and dermatitis herpetiformis) • Alopecia areata • Lichen planus • Sweet's syndrome • Localised Scleroderma (Morphoea)

Vasculitides
 
 • Large vessels vasculitis including: giant cell arteritis such as Takayasu's arteritis and temporal arteritis. • Medium sized and/or small vessels vasculitis including: polyarteritis nodosa, Kawasaki's 	
Blood disorders
 
 • Autoimmune hemolytic anemia • Autoimmune thrombocytopenia • Antiphospholipid syndrome • Pernicious anemia 	
Others
 
 • Autoimmune glomerulonephritis (including IgA nephropathy, glomerulonephritis rapidly progressive, membranous glomerulonephritis, membranoproliferative glomerulonephritis, and

disease, microscopic polyangiitis, Wegener's granulomatosis, Churg–Strauss syndrome (allergic granulomatous angiitis), Buerger's disease (thromboangiitis obliterans), necrotizing vasculitis and anti-neutrophil cytoplasmic antibody (ANCA) positive vasculitis (type unspecified), Henoch-Schonlein purpura, Behcet's syndrome, leukocytoclastic vasculitis.	
 • Autoimmune aplastic anaemia • Autoimmune neutropenia • Autoimmune pancytopenia 	
 • mesangioproliferative glomerulonephritis • Ocular autoimmune diseases (including autoimmune uveitis and autoimmune retinopathy) • Autoimmune myocarditis/cardiomyopathy • Sarcoidosis • Stevens-Johnson syndrome • Sjögren's syndrome • Idiopathic pulmonary fibrosis • Goodpasture syndrome • Raynaud's phenomenon
Liver disorders	Gastrointestinal disorders	Endocrine disorders

 • Autoimmune hepatitis • Primary biliary cirrhosis • Primary sclerosing cholangitis • Autoimmune cholangitis 	
 • Inflammatory Bowel disease, including Crohn's disease, ulcerative colitis, microscopic colitis, ulcerative proctitis • Celiac disease • Autoimmune pancreatitis 	
 • Autoimmune thyroiditis (including Hashimoto thyroiditis) • Grave's or Basedow's disease • Diabetes mellitus type I • Addison's disease • Polyglandular autoimmune syndrome • Autoimmune hypophysitis

When there is enough evidence to make any of the above diagnoses, the AE must be reported as a pIMD. Symptoms, signs or conditions which might (or might not) represent the above diagnoses, should be recorded and reported as AEs but not as pIMDs until the final or definitive diagnosis has been determined, and alternative diagnoses have been eliminated or shown to be less likely.

6.11 Meningitis

For the further evaluation of the safety signal of meningitis in the investigational vaccine groups all cases of meningitis occurring during the study will be reported as a SAE.

6.12 Events or outcomes not qualifying as adverse events or serious adverse events

6.13 Pregnancy

Female volunteers who are pregnant or intend to become pregnant will not be enrolled. Female subjects who become unexpectedly pregnant during of vaccination period (M0 to M2) must not receive additional doses of study vaccines but may continue other study procedures at the discretion of the investigator. While pregnancy itself is not considered an AE or SAE, any adverse pregnancy outcome or complication or elective termination of a pregnancy for medical reasons will be recorded and reported as an AE or a SAE.

The following should always be considered as SAE

- Spontaneous pregnancy loss, including:
 - spontaneous abortion, (spontaneous pregnancy loss before/at 22 weeks of gestation)
 - ectopic and molar pregnancy

- stillbirth (intrauterine death of foetus after 22 weeks of gestation).
- Any early neonatal death (i.e. death of a live born infant occurring within the first 7 days of life).
- Any congenital anomaly or birth defect identified in the offspring of a study subject (either during pregnancy, at birth or later) regardless of whether the foetus is delivered dead or alive. This includes anomalies identified by prenatal ultrasound, amniocentesis or examination of the products of conception after elective or spontaneous abortion.

Furthermore, any SAE occurring as a result of a post-study pregnancy AND considered by the investigator to be reasonably related to the investigational vaccines will be reported. While the investigator is not obligated to actively seek this information from former study participants, he/she may learn of a pregnancy through spontaneous reporting.

6.14 Detecting and recording adverse events and serious adverse events

6.15 Recording adverse events, serious adverse events and pregnancies

All AEs must be recorded into the appropriate section of the CRF, irrespective of intensity or whether or not they are considered vaccination-related.

6.16 Post-Study adverse events and serious adverse events

Investigators are not obligated to actively seek AEs or SAEs in former study participants. However, if the investigator learns of any SAE at any time after a subject has been discharged from the study, and he/she considers the event reasonably related to the investigational vaccines, the investigator will promptly notify the Study Contact for Reporting SAEs.

6.17 Active questioning to detect adverse events and serious adverse events

As a consistent method of collecting AEs, the subject should be asked a non-leading question such as:

'Have you felt different in any way since receiving the vaccines or since the previous visit?'

When an AE/SAE occurs, it is the responsibility of the investigator to review all documentation (e.g. hospital progress notes, laboratory and diagnostics reports) relative to the event. The investigator will attempt to establish a diagnosis pertaining to the event based on signs, symptoms, and/or other clinical information. In such cases, the diagnosis should be documented as the AE/SAE and not the individual signs/symptoms.

6.18 Assessment of intensity

The intensity of the following solicited AEs will be assessed as described:

Intensity scales for solicited symptoms in adults

Adults		
Adverse Event	Intensity grade	Parameter
Pain at injection site	0	None
	1	Mild: Any pain neither interfering with nor preventing normal every day activities.
	2	Moderate: Painful when limb is moved and interferes with every day activities.
	3	Severe: Significant pain at rest. Prevents normal every day activities.
Redness at injection site		Record greatest surface diameter in mm
Swelling at injection site		Record greatest surface diameter in mm
Fever*		Record temperature in °C/°F
Headache	0	Normal
	1	Mild: Headache that is easily tolerated
	2	Moderate: Headache that interferes with normal activity
	3	Severe: Headache that prevents normal activity
Fatigue	0	Normal
	1	Mild: Fatigue that is easily tolerated
	2	Moderate: Fatigue that interferes with normal activity
	3	Severe: Fatigue that prevents normal activity
Gastrointestinal symptoms (nausea, vomiting, diarrhoea and/or abdominal pain)	0	Normal
	1	Mild: Gastrointestinal symptoms that are easily tolerated
	2	Moderate: Gastrointestinal symptoms that interfere with normal activity
	3	Severe: Gastrointestinal symptoms that prevent normal activity

*Fever is defined as temperature $\geq 37.5^{\circ}\text{C}$ / 99.5°F for oral, axillary or tympanic route, or $\geq 38.0^{\circ}\text{C}$ / 100.4°F for rectal route. The preferred route for recording temperature in this study will be oral.

The maximum intensity of local injection site redness and swelling will be scored as follows:

0	:	0 mm
1	:	> 0 to \leq 50 mm
2	:	> 50 mm to \leq 100 mm
3	:	> 100 mm

The maximum intensity of fever will be scored as follows:

0	:	< 37.5°C (< 99.5°F)
1	:	$\geq 37.5^{\circ}\text{C}$ ($\geq 99.5^{\circ}\text{F}$) to $\leq 38.0^{\circ}\text{C}$ (100.4°F)
2	:	> 38.0°C (> 100.4°F) to $\leq 39.0^{\circ}\text{C}$ (102.1°F)
3	:	> 39.0°C (102.1°F)

The investigator will assess the maximum intensity that occurred over the duration of the event for all unsolicited AEs (including SAEs) recorded during the study. The assessment will be based on the investigator's clinical judgment.

The intensity should be assigned to one of the following categories:

- 1 (mild) = An AE which is easily tolerated by the subject, causing minimal discomfort and not interfering with everyday activities.
- 2 (moderate) = An AE which is sufficiently discomforting to interfere with normal everyday activities.
- 3 (severe) = An AE which prevents normal, everyday activities. In adults, such an AE would, for example, prevent attendance at work/school and would necessitate the administration of corrective therapy.

An AE that is assessed as Grade 3 (severe) should not be confused with a SAE. Grade 3 is a category used for rating the intensity of an event; and both AEs and SAEs can be assessed as Grade 3.

The normal ranges and toxicity grading for laboratory safety parameters used in this study: Adverse event	Intensity grade	Intensity*
Haemoglobin (males)	Normal range	12.5 - 17.0 g/dl
	1	< 12.5 but \geq 11.0 g/dl
	2	< 11.0 but \geq 10.0 g/dl
	3	< 10.0 g/dl
Haemoglobin (females)	Normal range	11.5 - 15.0 g/dl
	1	< 11.5 but \geq 10.5 g/dl
	2	< 10.5 but \geq 9.5 g/dl
	3	< 9.5 g/dl
Increase in leukocytes (WBC)	Normal range	3200 - 10799 cells/mm ³
	1	10800 - 15000 cells/mm ³
	2	15001 - 20000 cells/mm ³
	3	> 20001 cells/mm ³
Decrease in leukocytes (WBC)	Normal range	3200 - 10800 cells/mm ³
	1	2500 - 3199 cells/mm ³
	2	1500 - 2499 cells/mm ³
	3	< 1500 cells/mm ³
Decrease in platelets	Normal	140000 - 400000 cells/mm ³
	1	125000 - 139000 cells/mm ³
	2	100000 - 124000 cells/mm ³
	3	< 100000 cells/mm ³
Alanine Aminotransferase	Normal range	Below ULN (60 U/l for males; 40 U/l for females)
	1	1.1 - 2.5 x ULN
	2	2.6 - 5 x ULN
	3	> 5 x ULN
Aspartate Aminotransferase	Normal range	Below ULN (40 U/l for males; 35 U/l for females)
		1.1 - 2.5 x ULN
		2.6 - 5 x ULN
		> 5 x ULN
Creatinine (males)	Normal range	0.5 - 1.39 mg/dl
	1	1.4 - 1.79 mg/dl
	2	1.8 - 2.0 mg/dl
	3	> 2.0 mg/dl
Creatinine (females)	Normal range	0.5 - 1.29 mg/dl
	1	1.3 - 1.69 mg/dl
	2	1.7 - 1.9 mg/dl
	3	>1.9 mg/dl

ULN: upper limit of normal range

The normal ranges and toxicity grading for laboratory safety parameters used in this study: Adverse event	Intensity grade	Intensity*
--	-----------------	------------

6.19 Assessment of causality

The investigator is obligated to assess the relationship between investigational vaccines and study antimalarial medications and the occurrence of each AE/SAE. The investigator will use clinical judgment to determine the relationship. Alternative plausible causes, such as natural history of the underlying diseases, concomitant therapy, other risk factors, and the temporal relationship of the event to the investigational vaccines and study antimalarial medications will be considered and investigated. The investigator will also consult the IB and/or Summary of Product Characteristics to determine his/her assessment.

There may be situations when a SAE has occurred and the investigator has minimal information. However, it is very important that the investigator always makes an assessment of causality. The investigator may change his/her opinion of causality in light of follow-up information and update the SAE information accordingly. The causality assessment is one of the criteria used when determining regulatory reporting requirements.

In case of concomitant administration of vaccine and study antimalarial medication, it may not be possible to determine the causal relationship of general AEs to the individual vaccine or medication administered. All solicited local (injection site) reactions will be considered causally related to vaccination. Causality of all other AEs should be assessed by the investigator using the following question:

Is there a reasonable possibility that the AE may have been caused by the investigational vaccine or study antimalarial medications?

- YES : There is a reasonable possibility that the vaccines or study antimalarial medications contributed to the AE.
- NO : There is no reasonable possibility that the AE is causally related to the administration of the study vaccines or study antimalarial medications. There are other, more likely causes and administration of the study vaccines and study antimalarial medications is not suspected to have contributed to the AE.

If an event meets the criteria to be determined as 'serious', additional examinations/tests will be performed by the investigator in order to determine ALL possible contributing factors for each SAE.

Possible contributing factors include:

- Medical history.
- Other medication.
- Protocol required procedure.
- Other procedure not required by the protocol.
- Lack of efficacy of the vaccines, if applicable.
- Erroneous administration.
- Other cause (specify).

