6.21 Safety (ANALYSIS)

- Safety and reactogenicity of the investigational vaccine for each vaccination schedule:
 - Occurrence of solicited local and general AEs within seven days (day of vaccination and six subsequent days) after each vaccination.
 - Occurrence of unsolicited AEs from the date of the first vaccination to 29 days after the last vaccination, according to the Medical Dictionary for Regulatory Activities (MedDRA) classification.
 - Occurrence of SAEs (all, fatal, related to investigational vaccine) within 30 days (day of vaccination and 29 subsequent days) after each vaccination, according to the MedDRA classification.
 - Occurrence of SAEs (all, fatal, related to investigational vaccine) during the whole study period according to the MedDRA classification.
 - Occurrence of AEs and SAEs leading to withdrawal from further vaccination from Dose 1 (Day 0) up to study conclusion (Day 180), according to the MedDRA classification, for each vaccinated subjects.
 - Occurrence of pIMDs from Dose 1 (Day 0) up to study conclusion (Day 180), according to the MedDRA classification, for each vaccinated subjects.
 - Occurrence of meningitis from Dose 1 (Day 0) up to study conclusion (Day 180), according to the MedDRA classification, for each vaccinated subjects.

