6.22 Analysis of safety

The percentage of subjects with at least one local AEs with at least one general AE (solicited and unsolicited) and with any AE during the 7-day or total follow-up period up to 29 days after the last vaccine dose and overall will be tabulated with exact 95% CI. The percentage of doses followed by at least one local AE (solicited and unsolicited), by at least one general AE (solicited and unsolicited) and by any AE during the 7-day or the total follow up period up to 29days after the last vaccine will be tabulated with exact 95% CI. The same computations will be done for Grade 3 AEs, for any AEs considered related to vaccination and for any Grade 3 AEs considered related to vaccination.

The percentage of subjects reporting each individual solicited local AE (any grade and Grade 3) and solicited general AE (any grade, Grade 3, any related, Grade 3 related, resulting in medically attended visit) during the 7-day follow-up period (Day 0-6) after each vaccine dose and overall will be tabulated for each group. Similarly, the percentage of doses followed by each individual solicited local and general AE will be tabulated, overall vaccination course, with exact 95% CI.

For fever, the number and percentage of subjects reporting fever by half degree (°C) cumulative increments during the first seven days (Day 0-6) after each vaccine dose and overall will be tabulated. Similar tabulations will be performed for any fever with a causal relationship to vaccination and Grade 3 (> 39.5°C) causally related fever.

The percentage of subjects reporting unsolicited AEs from the date of the first vaccine dose up to 29 days after the last vaccine dose and after the sporozoite challenge will be tabulated by group and by MedDRA preferred term with exact 95% CI. Similar tabulation will be done for Grade 3 unsolicited AEs, for any causally related unsolicited AEs and for Grade 3 causally related unsolicited AEs.

The percentage of subjects reporting SAEs and pregnancies will be described in detail.

The percentage of vaccinated subjects reporting AEs of specific interest (meningitis and pIMDs) will be described in detail.

Biochemistry (ALT, AST and creatinine) and haematological (haemoglobin, WBC and platelets) laboratory values will be presented according to toxicity grading scales and tabulated by group.

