7 HOLDING RULES AND SAFETY MONITORING

7.1. No group holding rules will be pre-defined considering the evidence for a favourable safety profile of this candidate vaccine in Phase III infant evaluation.

7.2. Individual subject holding rules. Individual study participants who present at least one of the following stopping rules for individual subjects will be withdrawn from further vaccination:

- a) Local reactions: upon investigator discretion.
- b) Systemic solicited adverse events: The subject develops a Grade 3 systemic solicited adverse event beginning within 2 days after vaccination (day of vaccination and one subsequent day) and persisting at Grade 3 for >2 consecutive days.
- c) Unsolicited adverse events: The subject has any Grade 3 adverse event considered related to vaccination, persisting at Grade 3 for >2 consecutive days.

- d) The subject has a serious adverse event considered related to vaccination.
- e) The subject has an acute allergic reaction or anaphylactic shock following the administration of vaccine investigational product.
- f) Laboratory adverse events: The subject has any Grade 3 laboratory adverse event considered related to vaccination.

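### One combined YES/NO on causality (vaccine or antimalarials) feeds safety tables and holding rules worded as related to vaccination, with no stated mapping for Groups 4, 6 and 7

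*Protocol*

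**What the plan says.** Protocol 6.19 sets aside one class of event by rule: "All solicited local (injection site) reactions will be considered causally related to vaccination". For the rest, "Causality of all other AEs should be assessed by the investigator using the following question", and the question is "Is there a reasonable possibility that the AE may have been caused by the investigational vaccine or study antimalarial medications". The answer is YES or NO, and YES is defined as "There is a reasonable possibility that the vaccines or study antimalarial medications contributed to the AE". The section gives a reason for joining the two products. When they are given together, "it may not be possible to determine the causal relationship of general AEs to the individual vaccine or medication administered".

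Three later places use relatedness:

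- Section 6.21 lists "Occurrence of SAEs (all, fatal, related to investigational vaccine) during the whole study period", and the same categories for the 30 days after each dose.
- Section 6.22 repeats its AE percentages "for any AEs considered related to vaccination and for any Grade 3 AEs considered related to vaccination". It does the same for fever causally linked to vaccination, and adds related rows for solicited general and unsolicited AEs without naming a product.
- Section 7.2 withdraws a participant from further vaccination under rule (c), a Grade 3 unsolicited event related to vaccination that persists; rule (d), a related SAE; and rule (f), "The subject has any Grade 3 laboratory adverse event considered related to vaccination".

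Antimalarials go only to Groups 4, 6 and 7, starting on the day of vaccination (4.8.4 and 5.1.2).

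**The concern.** The recorded answer is about either product, while the tables and three holding rules ask about the vaccine alone. In Groups 1, 2, 3 and 5 no study antimalarial is given, so a YES can only mean the vaccine. In Groups 4, 6 and 7 it means the vaccine, the drugs or both. Unless something further is recorded, one row of a by-group table measures different things in different columns, and adding the drugs can appear to raise vaccine-related reactions when it has changed nothing about the vaccine.

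The overlap is not hypothetical. Section 4.7.3 lists gastrointestinal upset and headache among the main side effects of DHA-PIP, and both are solicited general AEs.

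This is also a matter of data capture. A statistical analysis plan can relabel a row, but it cannot recover an attribution that was never recorded.

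**Working it through.** **1. What is recorded against what is used**

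| Place | Product to which relatedness refers |
|---|---|
| 6.19, question and definition of YES | vaccine or antimalarials, combined |
| 6.21, SAEs | investigational vaccine |
| 6.22, AEs, Grade 3 AEs, fever | vaccination |
| 6.22, solicited general and unsolicited related rows | not named |
| 7.2(c), (d), (f) | vaccination |

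No section links the first line to the others.

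**2. How much of the trial is exposed** (group sizes and doses from Table 3, drug rounds from 5.1.2)

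- Participants: 30 + 30 + 30 = 90 of 190, or 47%.
- All vaccinations, Groups 1 to 7: 60 + 60 + 90 + 90 + 90 + 90 + 60 = 540.
- Vaccinations given with a drug round: Group 4, 30 × 3 = 90; Group 6, 30 × 3 = 90; Group 7, 30 × 2 = 60. The total is 240 of 540, or 44%.

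**3. Illustration of size**

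The protocol states no related-event rate, so there is no figure to reproduce. Let d be the chance that a participant has a drug-caused event of a given type, and v the chance of a vaccine-caused one. If the causes are independent, the combined question gives

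P(YES) = 1 − (1 − v)(1 − d),

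which exceeds v by (1 − v)d. Section 4.7.3 puts DHA-PIP side effects other than dizziness generally below 10% and often below 5%, so d = 5% and 10% are used. The values of v are assumptions.

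| v (assumed) | excess, d = 5% | excess, d = 10% |
|---|---|---|
| 0% | 5.0 points | 10.0 points |
| 10% | 4.5 | 9.0 |
| 30% | 3.5 | 7.0 |
| 50% | 2.5 | 5.0 |

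In a group of 30, the expected number of drug-caused events of one type is 30 × 0.05 = 1.5 to 30 × 0.10 = 3.0. The chance of at least one is 1 − 0.95^30 = 79% to 1 − 0.90^30 = 96%.

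**4. What does not depend on the combined answer**

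- Solicited local reactions are attributed to the vaccine by rule.
- The primary safety outcome in 4.2 is occurrence of SAEs, with no causality condition.
- The all-cause AE tables in 6.22, by participant and by dose, use no causality answer.
- Holding rule (a) is investigator discretion, (b) applies to Grade 3 systemic solicited events whatever their cause, and (e) concerns allergic reaction after the vaccine.

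**The case against.** The protocol discloses the difficulty: with same-day administration, attribution of a general AE to one product may be impossible, and a combined question is a cautious response. Many gastrointestinal and headache events would be YES to both on a split form. This stands in part. But 6.19 says only that separation may be impossible, not that it always is. A combined answer discards attribution even where it is clear, and if separation really were impossible, the labels in 6.21, 6.22 and 7.2 would be wrong.

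The CRF is not shown, and 6.19 opens by obliging the investigator to assess the relationship to both vaccines and antimalarials, so a split field may exist. This also stands. A reader might infer that drug reactions will be counted as vaccine reactions; the documents support only that they can be, because the mapping is unstated. The list of contributing factors in 6.19 does not close the gap: it covers SAEs only and does not separate study vaccine from study antimalarials.

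The reach is limited. The between-arm safety comparisons in section 3 are Groups 1 vs 2, 1 vs 5 and 2 vs 5, none of which receives drugs; the objectives involving Groups 4, 6 and 7 concern serologic response. For the holding rules, solicited gastrointestinal symptoms and headache come under rule (b), which ignores cause. Rule (c) covers unsolicited events at persistent Grade 3, (d) needs an SAE and (f) a Grade 3 laboratory event. The protocol gives no frequency for any of these. All of this stands and confines the effect to the descriptive related rows and three narrow rules.

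A reader might also infer that a triggered holding rule loses Month 3 antibody data in the drug arms. Section 4.11 allows immunogenicity follow-up after vaccination stops, and 8.4 keeps incomplete courses in the intention-to-treat analysis. What is lost is the full regimen and per-protocol inclusion.

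**Conclusion.** The mismatch holds. Section 6.19 specifies a combined answer, 6.21, 6.22 and 7.2(c), (d) and (f) call for a vaccine-specific one, and no rule connects them. In Groups 4, 6 and 7 drug-only events can enter the vaccine-related rows, so those rows are not comparable with Groups 1, 2, 3 and 5.

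The documents do not give the size. The 2.5 to 10 point range is an illustration that rests on independent causes, drug rates of 5% to 10% and an assumed vaccine-only rate of 0% to 50%. The drug rates are ceilings, and they are quoted for a product described as malaria treatment, not specifically for healthy volunteers. Extending the range to 12 points would mean using the dizziness rate, which is not a solicited event here. A haemoglobin fall after primaquine is not a good example either, since 4.7.3 describes the single low dose as safe even in severe G6PD deficiency.

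This should be corrected because the lost attribution cannot be rebuilt later, but it does not threaten the primary SAE outcome or the stated between-arm safety comparisons.

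**What to change.** In 6.19 and on the CRF, replace the single question by two items: related to study vaccine (YES/NO), and related to study antimalarials (YES/NO, or not applicable in Groups 1, 2, 3 and 5). Both may be YES when the products cannot be separated. State in 6.21 and 6.22 that related to vaccination, or to the investigational vaccine, means the vaccine item; name the product in the rows that now say only related; and tabulate the antimalarial item for Groups 4, 6 and 7.

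Sections 6.19 and 7.2 must be reconciled by the sponsor as to which causality answer rules (c), (d) and (f) use, including for an event attributed only to the antimalarials. That is a clinical decision, and no answer is proposed here.

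The cost is one extra CRF field and a few sentences. Some events will still be YES to both, so the separation will be incomplete, but the table will show where it could be made.
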